3 STUDY OBJECTIVES

3.1 Primary Objective

The primary objective of this study is to evaluate the long-term safety and tolerability of AERT in patients with spasticity due to MS.

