- Dispense the study medication. The investigator will explain to the subject how to take the study medication and the regimen to be followed until the next visit ([Section 7.5](#)).
- The site will administer the first daily dose of study medication to the subject.
- Record any adverse events (AEs) that have occurred ([Section 9.7](#)).
- Record all concomitant medications/therapies the subject is currently taking ([Section 7.7](#)).
- Schedule the next study visit.

6.3 Visits 1, 2, 3, 5, and 6 – Weeks 2, 6, 14, 42, and 54

Assessments/procedures will include the following:

- Record vital sign measurements, including BP, heart rate, respiratory rate, and body temperature ([Section 9.2](#)).
- At Visits 2, 3, 5, and 6, collect blood and urine samples for hematology, serum chemistry, and urinalysis ([Section 9.5](#)). Subject should be fasting if possible.
- Collect a urine sample for pregnancy testing for women of childbearing potential ([Section 7.8](#)).
- Administer the C-SSRS ([Section 9.6.3](#)).
- Administer the USP questionnaire ([Section 9.6.2](#)).
- Dispense the study medication. The investigator will explain to the subject how to take the study medication and the regimen to be followed until the next visit ([Section 7.5](#)).
- Collect unused study medication, assess compliance, and study drug accountability ([Section 7.9](#)).
- Record any AEs that have occurred ([Section 9.7](#)).
- Record all concomitant medications/therapies the subject is currently taking ([Section 7.7](#)).
- Schedule the next study visit.

6.4 Visit 4 – Week 28

Assessments/procedures will include the following:

- Record weight ([Section 9.4](#)).

- Record vital sign measurements, including BP, heart rate, respiratory rate, and body temperature ([Section 9.2](#)).
- Collect blood and urine samples for hematology, serum chemistry, and urinalysis ([Section 9.5](#)). Subject should be fasting if possible.
- Perform a standard 12-lead ECG ([Section 9.6.1](#)).
- Collect a urine sample for pregnancy testing for women of childbearing potential ([Section 7.8](#)).
- Administer the C-SSRS ([Section 9.6.3](#)).
- Perform the TNmAS-MAL assessment ([Section 8.2](#)).
- Administer the EDSS assessment ([Section 8.3](#)).
- Administer the USP questionnaire ([Section 9.6.2](#)).
- Dispense the study medication. The investigator will explain to the subject how to take the study medication and the regimen to be followed until the next visit ([Section 7.5](#)).

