- Collect unused study medication, assess compliance, and study drug accountability ([Section 7.9](#)).
- Record any AEs that have occurred ([Section 9.7](#)).
- Record all concomitant medications/therapies the subject is currently taking ([Section 7.7](#)).
- Schedule the next study visit.

6.5 Visit 7 End of Taper (Telephone Visit) – Week 56

- Record any AEs that have occurred ([Section 9.7](#)).
- Record all concomitant medications/therapies the subject is currently taking ([Section 7.7](#)).
- Schedule the final study visit.

6.6 Visit 8 (Final Visit or Early Termination) – Week 60

The assessments/procedures listed for Visit 8 (Final Visit) are to be completed by all subjects regardless of whether they complete the entire study or prematurely withdraw from the study. If the Final Visit is performed before Week 60 due to early termination of the subject, every effort should be made to perform the clinical evaluations as follows, especially blood sampling for hematology and serum chemistry, urinalysis, ECG, and the 2-week study drug taper. Assessments/procedures will include the following:

- Record weight ([Section 9.4](#)).

- Record vital sign measurements, including BP, heart rate, respiratory rate, and body temperature (Section 9.2).
- Collect blood and urine samples for hematology, serum chemistry, and urinalysis (Section 9.5). Subject should be fasting if possible.
- Perform a standard 12-lead ECG (Section 9.6.1).
- Collect a urine sample for pregnancy testing for women of childbearing potential (Section 7.8).
- Administer the C-SSRS (Section 9.6.3).
- Perform the TNmAS-MAL assessment (Section 8.2).
- Administer the EDSS assessment (Section 8.3).
- Administer the PGIC questionnaire (Section 8.1).
- Administer the USP questionnaire (Section 9.6.2).
- Collect unused study medication, assess compliance, and study drug accountability (Section 7.9).
- Record any AEs that have occurred (Section 9.7).
- Record all concomitant medications/therapies the subject is currently taking (Section 7.7).

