9.6 Other Safety Assessments

9.6.1 Electrocardiograms

A standard 12-lead ECG will be performed on subjects in the supine position. Subjects will have rested in the supine position for at least 5 minutes prior to the ECG. The time at which the subject assumed the supine position will be recorded to confirm the rest time. ECGs will be done at the visits specified in Table 1.

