4.2. Study Endpoints

4.2.1. Safety Endpoints

Safety endpoints include the following:

- Adverse events
- Vital signs
- Clinical laboratory tests
- 12-lead electrocardiograms (ECGs)
- Urinary Symptom Profile - USP© questionnaire (USP)
- Columbia-Suicide Severity Rating Scale (C-SSRS)

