10.6. Other Safety Measures

C-SSRS results will be presented in subject data listings.

USP summary scores (stress urinary incontinence score, overactive bladder score, and low stream score) will be summarized descriptively by time point for the observed value as well as for the change from baseline value. All USP data (including the 10 individual questions) will be presented in listings.

ECG parameters will be summarized descriptively by time point for the observed value as well as for the change from baseline value. All ECG data will be presented in listings.

No other safety analyses have been prospectively defined. If, however, after study results are reviewed, or the DSMB or Sponsor recommend additional safety parameters or analyses be completed, they will be fully described and documented in the final clinical study report. The SAP does not need to be amended to complete any other safety measures identified as post-hoc.

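### No 12-lead ECG is scheduled on drug after Week 28: the last one is at Week 60, about 4 weeks after the taper ends, and the SAP does not mark it as off drug

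*Protocol*

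**What the plan says.** Protocol 3.1 reads: "The primary objective of this study is to evaluate the long-term safety and tolerability of AERT in patients with spasticity due to MS". SAP 4.2.1 lists six safety endpoints: adverse events, vital signs, clinical laboratory tests, 12-lead ECGs, the USP questionnaire and the C-SSRS.

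The timing of ECGs is left to the schedule of assessments. Protocol 9.6.1 says "ECGs will be done at the visits specified in Table 1". Table 1 places them at Screening (de novo subjects) or Baseline (rollover subjects), at Visit 4 (Week 28) and at Visit 8 (Week 60). The visit text agrees: "Perform a standard 12-lead ECG" is in Section 6.4 for Week 28 and in Section 6.6 for Week 60. Section 6.3, which covers "Visits 1, 2, 3, 5, and 6" (Weeks 2, 6, 14, 42 and 54), has no ECG. SAP Table 1 has the same ECG pattern.

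Other safety tests are taken at Week 54. Section 6.3 includes vital signs, C-SSRS and USP, and adds: "At Visits 2, 3, 5, and 6, collect blood and urine samples for hematology, serum chemistry, and urinalysis".

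Protocol 7.5 puts the end-of-treatment taper at Weeks 54 to 56. Visit 7 (Week 56) is a telephone call. Section 7.1.1 exempts subjects who reach only 40 mg/day from the taper phase.

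For analysis, SAP 10.6 says: "ECG parameters will be summarized descriptively by time point for the observed value as well as for the change from baseline value". It does not separate on-drug from off-drug time points.

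**The concern.** A study of long-term safety should observe each of its safety endpoints late in treatment, while subjects are still taking the drug. Five of the six are observed at Week 54, the last clinic visit before the taper, or continuously in the case of adverse events. The ECG is not. Its only scheduled on-drug observation is about halfway through, and its last observation comes after the drug has stopped.

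An ECG change that arises after Week 28, causes no symptoms and reverses when the drug stops would not be found by any scheduled ECG. A change present at Week 28 and gone at Week 60 could have resolved during treatment or because treatment ended, and the two scheduled values cannot tell these apart. The unlabelled Week 60 row makes that harder for a reader of the tables to notice.

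The documents describe the study as a source of 1-year data at 80 mg/day. Protocol 11.3 says that the earlier 1-year study (OS440-3003) used 40 mg/day, and it seeks 50 subjects treated for 1 year at 80 mg/day here.

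**Working it through.** There is no sample-size formula to reproduce, because Protocol 11.3 gives no statistical rationale for the number of subjects. The check is day arithmetic on the visit schedule.

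**1. Reproduce the plan's calendar** (durations from Protocol 4.1).
- Titration plus maintenance: 9 + 52 × 7 = 373 days. The visit calendar puts the start of the taper at Week 54 = 54 × 7 = 378 days. The difference is 5 days, or 1.3%.
- Adding the 14-day taper: 373 + 14 = 387 days, against Week 56 = 392 days.
- The two counts agree closely enough. The visit calendar is used below.

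**2. Where the ECGs fall.**
- Visit 4: 28 × 7 = Day 196, which is 196/378 = 52% of the way to Week 54.
- Week 28 to Week 54: 378 − 196 = 182 days = 26 weeks with no further scheduled ECG. To the end of the taper it is 392 − 196 = 196 days = 28 weeks.
- Visit 8: 60 × 7 = Day 420.

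**3. From end of dosing to the last ECG, subjects who taper.**
- Nominal: 420 − 392 = 28 days.
- With windows (Visit 6 ± 3 days, a 14-day taper starting from that visit, Visit 8 ± 3 days): Visit 6 is Day 375 to 381, the taper ends Day 389 to 395, and Visit 8 is Day 417 to 423. The gap is 417 − 395 = 22 days at the shortest and 423 − 389 = 34 days at the longest.
- From the stated durations instead: 420 − 387 = 33 days, within that range.

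**4. Subjects maintained only on 40 mg/day (no taper).**
- Nominal: 420 − 378 = 42 days = 6 weeks.
- With windows: 417 − 381 = 36 to 423 − 375 = 48 days.

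**5. Endpoint by endpoint at Week 54** (Table 1 and Section 6.3).

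| SAP safety endpoint | Planned on-drug observation at Week 54 |
|---|---|
| Adverse events | Yes, and throughout |
| Vital signs | Yes |
| Laboratory tests | Yes |
| USP | Yes |
| C-SSRS | Yes |
| 12-lead ECG | No |

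Each completer has one scheduled on-drug ECG after dosing starts and none at 1 year.

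**6. How the SAP treats off-drug values.** SAP 10.1 counts an adverse event as treatment-emergent only up to the last dose, and SAP Section 12 records that an earlier 30-day window was removed. The SAP therefore already separates on-drug from post-drug data for adverse events, but not for ECGs in 10.6.

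SAP 7.3.3 adds a second route for mixing. It assigns early-termination data to the closest scheduled visit. Table 1, footnotes 2 and 6, has early withdrawers taper for 2 weeks and complete the Visit 8 evaluations. A subject who starts that taper at Week 26 and leaves before Visit 4 finishes it at Week 28 (26 + 2). An exit ECG taken soon afterwards is off drug but closest to Visit 4, so it would enter the Week 28 row.

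**The case against.** The strongest reply is that this is a design choice and not an error. The protocol and SAP agree with each other on ECG timing, and neither promises a 1-year on-drug ECG. The documents report no ECG signal. The drug-specific risks they name are urinary symptoms (Protocol 9.6.2) and orthostatic hypotension (9.2), and both are monitored through Week 54. Whether a second on-drug ECG is needed may depend on the Investigator's Brochure and earlier studies, which are not available here. An off-drug ECG also has a use: it can show whether a Week 28 change reversed. All of this stands, and it is why the point is an inexpensive improvement and not a defect that invalidates the study.

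Three stronger readings are tempting, and the documents do not support them.

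- **A late ECG effect cannot be seen at all.** Protocol 9.7.1 calls for relevant evaluations when an adverse event is suspected, so a symptomatic effect can prompt an ECG. Heart rate is measured at Weeks 42 and 54. Some early terminators may also have an ECG while still on drug. What is lost is scheduled detection of asymptomatic, reversible changes arising after Week 28.
- **The long-term safety objective has no 1-year on-drug data.** Five of the six endpoints do. The gap concerns the ECG alone, and even there the Week 28 ECG is useful: the plan seeks at least 100 subjects treated for 6 months.
- **The final row will be used to claim 1-year ECG safety.** Neither document plans such a statement, and a careful reader can work out from the taper dates that Week 60 is off drug. The missing label is a reporting weakness and no more.

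It is also tempting to state what event rate a Week 54 ECG in 50 subjects could exclude. The SAP defines no ECG outlier criterion, so no such bound is offered.

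**Conclusion.** The point holds for the ECG endpoint. After baseline the only scheduled ECGs are at Week 28, on drug, and at Week 60, nominally 28 days after the end of the taper (22 to 34 days with windows; about 6 weeks without a taper). Twenty-six weeks of dosing up to Week 54 follow the last scheduled on-drug ECG, and the 50 subjects sought for 1 year at 80 mg/day contribute no planned 1-year on-drug ECG. SAP 10.6 presents the Week 60 values without marking them as off drug, and SAP 7.3.3 can move off-drug exit ECGs into the Week 28 row.

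This assumes that visits follow the Table 1 calendar and that the taper starts at Visit 6 and lasts 14 days. It counts only scheduled ECGs after open-label dosing begins, and it does not assume that arbaclofen affects the ECG. The change is worth making because the objective is long-term safety and the remedy uses a clinic visit that already exists.

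**What to change.** - **Protocol Table 1, Sections 6.3 and 6.6, and SAP Table 1:** take completers' final 12-lead ECG at Visit 6 (Week 54), before the taper starts, instead of at Visit 8. Keep the Visit 8 ECG for early terminators, and reword Section 6.6, which now asks all subjects for every Visit 8 assessment.
- **SAP 10.6:** summarize Weeks 28 and 54 as the on-drug rows, and label any Week 60 ECG as post-treatment.
- **SAP 7.3.3:** exempt ECGs taken after the last dose from assignment to the closest scheduled visit, so that off-drug early-termination ECGs stay out of the on-drug rows.

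**Cost.** A protocol amendment and short SAP edits, with no added visits and no added ECGs. Completers lose a routine off-drug ECG that could show reversibility. If the sponsor prefers to keep both, the cost is one extra ECG per completer. If the visits have already taken place, the two changes to SAP 10.6 and 7.3.3 can still be made: they need only ECG dates and the last-dose date, which SAP 10.1 already uses to define treatment-emergent events.

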7 STUDY TREATMENTS

7.1 Treatments Administered

All subjects will begin treatment with AERT at 40 mg per day (2 x 20 mg) for 3 days, then increase to 60 mg per day (3 x 20 mg) for 3 days, and then increase to 80 mg per day (4 x 20 mg). Once the subject has reached the maintenance dose, they will remain on that dose for approximately 1 year (Figure 2). The maintenance dose will be the highest tolerated dose, not exceeding 80 mg per day. The description of study drug kits and treatments is shown below in Table 2. Subjects may choose to taper study drug after Visit 3 if they experience adverse events. Direct consultation with the investigator site must be conducted before consideration for dose taper. Dose tapers should occur over the course of 9 days in 20 mg increments. Subjects should be encouraged to titrate back to 80 mg once adverse events subside or remain on the maximally tolerated AERT dose. Up to 3 dose tapers over the course of the clinical study are permitted.

Table 2: Study Drug Kits and Treatments, Study OS440-3005

Dosage form description:	Blue, round biconvex tablets.
Package description:	HDPE white bottles with 60 active 20-mg tablets.
Daily dose:	40, 60, and 80 mg arbaclofen depending on the study day. There will be a 9-day titration period (3 days at 40 mg/day, 3 days at 60 mg/day, and then increase to 80 mg/day), then an approximately 1-year maintenance period at 80 mg/day or the highest tolerated dose, followed by a 2-week taper period. Study tablets will be taken twice daily (BID).
Cumulative maximal dosage:	up to 28,420 mg arbaclofen
Manufacturer:	Osmotica Pharmaceutical US LLC, Marietta, GA 30062

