7.1.1 Treatment Administration

The study medications will be administered orally twice daily (every 12 hours, or BID) without regard to food. Note: For the 60 mg/day titration, this means 1 x 20 mg AERT in the morning and 2 x 20 mg AERT in the evening.

Once the subject has reached the maintenance dose, they will remain on that dose for approximately 1 year. The maintenance dose will be the highest tolerated dose, not exceeding 80 mg per day. All attempts should be made for subjects to titrate to the 80 mg per day dose. If subjects experience untoward tolerability issues due to AERT, they may taper study drug only under the guidance of the study site (i.e., in 20 mg increments per week). Subjects may subsequently attempt study drug taper if the investigator deems this clinically appropriate. There will be no taper phase for subjects who solely achieve a 40 mg per day maintenance dose. Subjects may attempt to titrate to the target dose of 80 mg per day, if tolerability issues have resolved.

If a subject misses 7 or more consecutive days of dosing AND has taken less than 80% of their doses of study medication in a 42-day (6-week) period, then the subject must be discontinued (see [Section 12.4](#)).

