7.4 Method of Assignment of Study Drug

[figure not shown]
This is an open-label study and all subjects will begin treatment with AERT at 40 mg per day (20 mg BID) for 3 days, then increase to 60 mg per day (20 mg in the morning and 2 x 20 mg in the evening) for 3 days, and then increase to 80 mg per day (2 x 20 mg BID). Once the subject has reached the maintenance dose, they will remain on that dose for approximately 1 year. The maintenance dose will be the highest tolerated dose, not exceeding 80 mg per day. Subject will be allowed to taper the 80-mg/day dose for issues of tolerability on at most three occasions. If tolerability issues persist, the subject will be required to discontinue from the study.

After Baseline procedures have been completed, authorized site personnel will acknowledge that the applicable subject met all the specified inclusion criteria ([Section 5.1](#)) and none of the exclusion criteria ([Section 5.2](#)) and an enrollment number will be sequentially assigned.

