7.5 Selection and Timing of Doses in the Study

There will be a 9-day titration period (3 days at 40 mg/day, 3 days at 60 mg/day, and 3 days at 80 mg/day), then a 1-year maintenance period, followed by a 2-week taper period. The maintenance dose will be the highest tolerated dose, not exceeding 80 mg per day. Subjects who discontinue early should also follow the 2-week taper period. Figure 2 presents the dosing regimen flowchart, including titration and taper, to be used during the study.

Figure 2: Flowchart of Open-Label Dosing Regimen, Study OS440-3005

At the end of treatment, a 2-week taper period will take place from Weeks 54 to 56. Subjects who discontinue early should also follow the 2-week taper period.

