12.4 Withdrawal of Subjects

Withdrawn subjects are those who do not complete all evaluations and procedures outlined in the protocol. Subject withdrawal requires a 2-week dose taper. A subject will be considered to have discontinued prematurely if he/she withdraws prior to completing Visit 8 (Final Visit). If a subject misses 7 consecutive days AND has taken less than 80% of their doses of study medication in a 42-day (6-week) period, then the subject must be discontinued. Subjects may also be withdrawn from the study because of any of the following:

- **Adverse Event:** An AE that, in the opinion of the investigator or Sponsor, suggests that continued participation in the study is not in the subject's best interest for safety reasons (also see [Section 10](#)). All AEs that are present when the subject withdraws from the study will be followed as described in [Section 9.7.4](#).
- **Medical Condition:** Any medical condition that, in the investigator's judgment, would increase the risk or interfere with the evaluation of study objectives.
- **Lost to Follow-up:** Confirmed at minimum by two phone calls and a traceable letter without answer.
- **Subject Request:** Subject requests for any reason to be withdrawn or withdraws his/her consent. Every effort should be made to determine the reason for the withdrawal request (e.g., AE, lack of efficacy, scheduling issues, etc.).
- **Protocol Deviation:** A subject may be withdrawn from the study at the discretion of the investigator or Sponsor due to poor compliance with protocol requirements that may compromise the study results or subject safety.
- **Enrollment in Another Study:** Enrollment in other protocols involving research drugs, medical devices, or surgeries.
- **Other Anti-spasticity Treatment:** Starting any other pharmacological anti-spasticity treatment during the study.

- **Relapse:** Subjects who experience an acute MS exacerbation/relapse (symptoms including but not limited to visual disturbance, dizziness, tingling, or extreme fatigue lasting greater than 24 hours and occurring at least 30 days after a previous relapse) requiring immediate therapy or adjustment in disease-modifying medication dose (e.g., oral or intravenous high-dose steroid therapy).

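### Two dose-taper instructions conflict: the pace of reductions for adverse events, and whether subjects who only reach 40 mg/day taper at all

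*Protocol*

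**What the plan says.** **Pace of a reduction for adverse events or tolerability.** Protocol 7.1: "Dose tapers should occur over the course of 9 days in 20 mg increments". Protocol 7.1.1, on tolerability problems with the same drug: "they may taper study drug only under the guidance of the study site (i.e., in 20 mg increments per week".

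**Subjects who never go above 40 mg/day.** Protocol 7.1.1: "There will be no taper phase for subjects who solely achieve a 40 mg per day maintenance dose". Protocol 12.4: "Subject withdrawal requires a 2-week dose taper". Protocol 7.5: "At the end of treatment, a 2-week taper period will take place from Weeks 54 to 56", and "Subjects who discontinue early should also follow the 2-week taper period". Table 1 footnote 6 repeats the two statements of 7.5. Table 1 footnote 2 sends subjects who withdraw early to Section 7.1 for their taper. There the narrative gives the 9-day pace, while Table 2 in the same section gives a 2-week taper.

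**Earliest time of a reduction.** Protocol 7.1: "Subjects may choose to taper study drug after Visit 3 if they experience adverse events". Section 7.1.1 states no earliest time. Section 7.4 gives only a maximum number: "Subject will be allowed to taper the 80-mg/day dose for issues of tolerability on at most three occasions".

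**Analysis.** SAP 10.1 tabulates adverse events by modal dose, and by dose at the time of the event, within titration, maintenance and taper periods. It treats events as treatment-emergent only up to the last dose and lists the others separately. SAP 7.4.1 gives 40 mg modal dose its own column. SAP 5.1 places the taper at Weeks 54 to 56. SAP 10.1 does not define where a period starts or ends.

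**The concern.** Sections 7.1 and 7.1.1 address the same decision, a dose reduction because the subject is not tolerating the drug, and give different paces. Sections 7.1.1 and 12.4 can both apply to the same person, a 40 mg subject who withdraws, and on their face one says no taper while the other says a taper is required. Site staff reading different sections could each believe they are following the protocol.

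These are participant-safety instructions, so the conflict matters whatever its statistical effect. It also reaches the primary objective, which is long-term safety and tolerability. Whether a 40 mg subject tapers decides when the last dose falls, which events count as treatment-emergent, and whether that subject appears in the taper-period tables.

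**Working it through.** The plan states no taper-related figure that settles the matter. The only total that depends on the taper is the cumulative maximum of 28,420 mg in Table 2. It cannot show which taper was intended, because 52 weeks at 80 mg/day already gives 364 × 80 = 29,120 mg before any titration or taper is added.

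**1. Pace.** Inputs: 20 mg steps (both sections), 9 days (7.1), one step per week (7.1.1), starting dose 80 mg/day.

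- With weekly steps, step *k* falls on day 7(*k* − 1) + 1. Step 2 (to 40 mg) is on day 8, step 3 (to 20 mg) on day 15 and step 4 (to 0) on day 22.
- 80 to 40 mg: day 8 lies inside 9 days, so the two rules can coincide if the steps fall on days 1 and 8.
- Three steps: day 15 lies outside 9 days however the 9 days are divided, so the rules cannot both be met.
- Duration over three levels: 3 × 3 = 9 days against 3 × 7 = 21 days. The equal 3-day split is an assumption. Figure 2 is not shown, and the text does not give the split.

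**2. 40 mg subjects.** The instructions side by side:

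| Place | Situation | Instruction | 40 mg exemption stated? |
|---|---|---|---|
| 7.1.1 | Only ever reached 40 mg/day | No taper phase | It is the exemption |
| 7.5; Table 1 footnote 6 | End of treatment; early discontinuation | 2-week taper | No |
| 12.4 | Withdrawal | 2-week taper required | No |
| Table 1 footnote 2 | Early withdrawal | Refers to 7.1 (9 days in the narrative, 2 weeks in Table 2) | Not in the footnote |

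For a 40 mg completer the last dose is at Week 54 without a taper and Week 56 with one: (56 − 54) × 7 = 14 days. An event starting in those 14 days is treatment-emergent in one case and only listed in the other.

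**3. Does pace move overall modal dose?** Take the permitted maximum of three tapers in a 364-day maintenance period, with prompt return to 80 mg (assumption).

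| Days per taper | Days in tapers | Share of 364 | Days at 80 mg |
|---|---|---|---|
| 9 | 27 | 7.4% | 337 |
| 14 | 42 | 11.5% | 322 |
| 21 | 63 | 17.3% | 301 |

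The modal dose is 80 mg in every row.

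**The case against.** **The 40 mg sentence may be a specific exception to a general rule.** Footnote 2 of Table 1 points to Section 7.1, and the exemption sits in its subsection 7.1.1. Table 2 lists daily doses of 40, 60 and 80 mg only, which would fit having no step below 40 mg. The sentence also sits in a paragraph on tolerability reductions, so it might not concern the end-of-treatment taper at all. These readings are reasonable, but they differ from one another and the text does not choose between them. Section 12.4 states a requirement with no exception.

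**The pace conflict may be small.** If no reduction goes below 40 mg, the longest taper from 80 mg has two steps and the rules can be made to agree. That stands as a limit on size. However, the text states no lowest dose for a taper, and nothing tells a site to place the steps on days 1 and 8.

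**Stronger readings that a reader might infer, and that the documents do not support:**

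- *That 80 to 40 mg takes 9 days under one rule and 14 under the other.* The 14 counts a further week after 40 mg has already been reached on day 8.
- *That the Visit 3 condition is a third contradiction, covering 14 of 54 weeks.* Section 7.1 sets a condition, and 7.1.1 and 7.4 are silent on timing. Silence does not negate a limit, and failing to titrate up is not the same as tapering down. This needs clarifying, but its share of the study does not measure a conflict.
- *That dose-at-event or overall modal-dose assignments will vary.* Dose at event follows the dosing record, so different practice shows up as real exposure and not as misassignment. Pace does not move the overall modal dose, as the last table shows.

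**The missing period boundaries in SAP 10.1 would be a gap even if the protocol were consistent.** This is correct. The protocol conflict adds to that gap for 40 mg subjects but does not create it.

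**Conclusion.** Two conflicts stand in the current protocol text.

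1. **Pace:** 9 days against weekly 20 mg steps for the same kind of reduction. They can be reconciled at two steps and not at three or more. At three levels the difference is 9 against 21 days, assuming equal 3-day levels within the 9 days.
2. **40 mg subjects:** no taper in one section and a 2-week taper in others, with no stated exemption. For a completer the last dose can differ by 14 days.

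Site practice can vary as a result; the documents do not show that it will. The analysis effect is confined to the taper-period adverse event tables and to the end of the treatment-emergent window for 40 mg subjects. How many subjects this touches is unknown, because the plan does not forecast how many will stay at 40 mg. Figure 2 may specify the taper doses, but it would not remove the contradictory text. The point needs correcting because it concerns how participants come off the drug, even though the study is descriptive and performs no tests.

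**What to change.** - Reconcile Protocol 7.1 (narrative and Table 2), 7.1.1, 7.5, 12.4 and Table 1 footnotes 2 and 6 into one consistent taper instruction, and check Figure 2 against it. It should give a single pace for reductions due to adverse events or tolerability, and say whether the 40 mg statement covers end of treatment, early discontinuation and withdrawal. Which rule is right is for the sponsor's clinical team; no view is offered here.
- Clarify whether the Visit 3 condition in 7.1 also governs the tolerability tapers in 7.1.1 and 7.4.
- In SAP 10.1, define the start and end of the titration, maintenance and taper periods to match the reconciled text. State where a mid-study taper is counted, and how 40 mg subjects with and without a taper enter the taper-period tables.

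The cost is a protocol clarification and one SAP definition. No new data, visits or subjects are needed.
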